All participants will be followed from randomization until the completion of the study (one year of lithium/placebo treatment). Participants will be followed as described in the Schedule of Visits (Table 6). Study assessments will be done at screening, baseline, every 10-14 days during the titration phase (in general, for up to six visits), and monthly until the end of study.

During the titration phase, participants will take the same dose of study medication for a minimum of 5 days prior to having their levels reassessed. Results from the blood draw are available to sites within approximately 3 days of the blood shipment, at which point a new dose may be selected and shipped to the participant if they are unavailable to pick up the prescription. Based on the dispensing of 2 weeks of study medication at a time and that it is necessary to allow a minimum of 4 days after a study visit for processing blood samples, communicating findings to the Central Psychiatrist/Safety Officer, communicating actual or simulated plasma levels to the study site, prescribing, and dispensing medications, there is a window of 10 to 14 days between titration visits. The Site Coordinator can conduct all assessments unless a physical exam is

required. Additionally, it is possible for participants to have unscheduled check-in visits at any time.

During titration phase, each new dose of study medication must be taken for a minimum of five days before collecting and sending another Lithium blood sample.

Steady State Visits

Once participants have reached steady state, study visits will occur every month, with a window from one week before the target date to one week afterwards. For the completion of the study, the window will be between one week before the target date to one month afterwards.

Ongoing Considerations and Special Circumstances

Additional visits will be completed as necessary for emergent events.

Pregnancy testing: At every visit post-randomization, participants of childbearing potential will be reminded of the potential dangers of lithium during pregnancy, review acceptable birth control methods, document what method of contraception is being used, and update all medications as well as over-the-counter medications, supplements being used.. If there is reason to doubt the participant's judgment, a pregnancy test will be done. Women of childbearing potential will have pregnancy testing at each study visit.

Participant Pregnancy:

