All study reports and journal manuscripts must be reviewed and approved by the MAVERIC CSPCC Director prior to submission for publication. After approval for submission is granted by the MAVERIC CSPCC Director, VA Central Office must be notified upon acceptance of any publications. This includes minor publications such as abstracts and poster presentations.

Planned Publications

A list of planned publications is provided below. The design paper will be completed during the conduct of the study. The manuscript detailing the main study results will be completed within six months of the study's completion.

1. Efficacy of lithium in the prevention of repeated suicide attempts in high risk subjects with affective disorders: A VA Cooperative Study (main publication that will present clinical outcomes)
2. Design, rationale and methodological challenges in a randomized placebo-controlled trial of lithium and enhanced usual care of persons with recent suicide attempts.
3. Determinants of treatment adherence to lithium in participants who recently attempted suicide.
4. Predictors of impulsive and non-impulsive suicide attempts. (Secondary aim b).
5. Predictors of repeated suicide attempts and suicide events (secondary aim c and d).

6. Effect of adjunctive lithium in managing symptoms of bipolar disorder and depression in patients who have survived a suicide attempt (secondary aim e)
7. Mediators and moderators of lithium augmentation on prevention of suicide reattempts (secondary aims b,f)
8. Relationship between lithium plasma levels and repeated suicide attempts in patients who have survived a suicide attempt

XXI. TABLES AND FIGURES

Table 1: Instruments and scales for data acquisition

Domain	Measure	Abbreviation	Description	Source	# items	Study Purpose	Time (minutes)
Suicidality	Columbia Suicide Severity Rating Scale-lifetime version, supplemented (Posner et al., 2011; Matarazzo et al., 2013)	CSSRS-lifetime-supp	History of suicide-related behaviors	Interview	39 (6 item screen)	Eligibility	20
	Columbia Scale -since last visit version, supplemented (Posner et al., 2011; Matarazzo et al., 2013)	CSSRS-last visit-supp	Interim history of suicide related behaviors	Interview	Variable (6 item screen)	Monitoring	10
	Suicide Intent Scale (Beck et al., 1974)	SIS	Context and characteristics of suicide attempts	Interview	15	Monitoring	8

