				T 1	T 2-3	T 4	T 5-6	M 2-5	M 6	M 7-8	M 9	M10,11	Early D/C			
Estimated time per visit	2 hrs	2 hrs	1.25hrs	1hr	45min	1.25hr	45min	1hr	1.25hr	1hr	1hr	1hr	1hr	1.75hr	1.75hr	30min
Phone contact allowed ⁺								Yes		Yes		Yes				Yes
Eligibility Screening																
Informed Consent ⁺⁺	X	X														
Review Incl/Excl. Criteria (S12)	X	X														
Demog. and military history (B02, B03)		X														
Medical history reviewed (B04)			X													
Psychiatric history reviewed (S01)	X		X													
Medications and treatments reviewed (S03)	X	X	X	X	X	X	X	X	X	X	X	X	X	X	X	X
MH Provider concurrence documentation obtained	X	(X)														
Primary Care Provider awareness documentation obtained ⁺⁺⁺	X	(X)														
Medical Assessments																
Physical Exam (B01)		X												X	X	
Vital Signs (B01, T04)		X	X	X	X	X	X	X	X	X	X	X	X	X	X	
EKG ⁺⁺⁺⁺ (S09)		X		X (once during titration)				X (once during steady state)						X	X	
Creatinine (S10, T02)		X		X	X	X	X	X	X		X			X	X	
CBC, electrolytes, calcium (S10, T01)		X				X			X					X	X	
TSH, T4 (S10, T02)		X				X			X					X	X	
Pregnancy test as appropriate (S10, T01)		X	X	X	X	X	X	X	X	X	X	X	X	X	X	
Interim history (B05)			X	X	X	X	X	X	X	X	X	X	X	X	X	X
Enrollment																

Randomization (S12)			X												
---------------------	--	--	---	--	--	--	--	--	--	--	--	--	--	--	--

Study Medication	Eligibility Evaluation	Eligibility Confirmation	BL	T 1	T 2-3	T 4	T 5-6	M 2-5*	M 6	M 7-8	M 9	M 10-11	Early D/C	End of Study	F/U (30 days)
Lithium level (T02)				X	X	X	X	X	X		X				
Adherence (T03, T05)				X	X	X	X	X	X	X	X	X	X	X	
Adverse events, (SAEs and AEs) (using lithium side effects checklist) (B13, T02)			X	X	X	X	X	X	X	X	X	X	X	X	X
Planned dose adjustment				X	X	X	X								
Dispense study medication++++			X	X	X	X	X	X	X	X	X	X	(X)	(X)	
Current Treatment Info.															
Medications (S03)	X		X	X	X	X	X	X	X	X	X	X	X	X	
VA record review	X		X	X	X	X	X	X	X	X	X	X	X	X	X
Service use based on the Cornell Service Index (B05)			X	X	X	X	X	X	X	X	X	X	X	X	X
Psychiatric Measures															
MINI (S11)	X														
PCL (B12)		X													
SCID SUD (S05)	X														
OMC (S06)	X														
UBACC (S04)	X														
CSSRS-lifetime version suppl with SIS for index attempt (S07, S08)	X														
CSSRS-last visit version supple with SIS f/u for attempts (B06, S08)		X	X	X	X	X	X	X	X	X	X	X	X	X	X
PHQ-9 (B07)			X	X		X		X	X	X	X	X	X	X	X
ISS (B08)			X	X		X		X	X	X	X	X	X	X	X
Audit C (B09)			X	X				Month 3	X		X		X	X	

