3.2. Description of the Intervention Strategy

Eligible patients who consent to participate will be randomized to receive Lithium or placebo. Initial dosage will be 600 mg /day of lithium (or matching placebo), to be titrated to achieve serum lithium level of 0.6 to 0.8 meq/liter. Mock serum lithium level for placebo patients will be calculated using Therapeutic Drug Monitoring method (Yukawa, 1993) based on age, weight, serum creatinine level, adherence, and side-effects. Titration visits will occur at intervals of 5-7 days over 3 months, with maximum allowed dosage not to exceed 1500mg.

Once the target serum lithium level has been reached the patient will be on steady state maintenance phase for the rest of the study with active participation and intervention terminating at 12 months after randomization.

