5.2. Secondary Endpoints

There are multiple secondary endpoints being considered for the study where endpoint events for secondary objectives #1, 2, and 5 will be assessed as time to event outcomes, endpoint events for secondary objective # 3 will be assessed as count data, and endpoint events for Secondary Objective #4 will be evaluated as a binary outcome.

For Secondary Objective #1, Time from randomization to death from any cause will be analyzed. Additionally, self-directed violence as described in section 4.2 will be classified further as either impulsive or non-impulsive attempt based on Beck Suicide Intent Scale, (Question#15 on CRF-Form S8), and will be analyzed separately. Lastly, non-suicidal self-directed violence behavior defined as the primary endpoint without the death from suicide will be considered as a separate outcome.

For Secondary Objective #2 which evaluates efficacy in different subgroups, the primary endpoint as described in section 4.2 will be analyzed.

The endpoint for Secondary Objective #3 considers all components of self-directed violence as described in section 4.2. Therefore, a combined total of all episodes of all components of the primary outcome will be an endpoint, and total counts of each component, in addition to all emergency department visits will be separate endpoints.

For Secondary Objective #4, dependent variables being considered longitudinally include (1) presence or absence of symptoms, and (2) presence or absence of suicidal ideation. Presence or absence of symptoms will be derived by the Internal State Scale (CRF-Form B8), and presence or absence of suicidal ideation will be derived from the Columbia Follow Up Questionnaire (CRF-Form B6).

Lastly, for Secondary Objective #5, the endpoint event will be the same as the primary endpoint described in section 4.2.

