5.3. Statistical Methods for Secondary Analyses

Secondary objective#1 will use a time to event, survival analysis to determine whether there is a treatment difference in event rates for each of the defined endpoints. The null hypothesis for each endpoint is that the two treatment groups do not differ in their hazard

rates. The alternative hypothesis is that the intervention group on lithium has a lower hazard rate than the placebo group. As with the primary analysis, log-rank test and Cox proportional hazards models will be used.

For secondary objective#2, the null hypothesis for each of the factors is that treatment effect does not differ over levels of the factor. The alternative hypothesis is that there is differential treatment effect over levels of the factor. Effect modification will be evaluated through regression methods. Cox proportional hazards regression model will include the treatment term, a term for the target factor, and the interaction term of the two. If the null hypothesis is rejected at $p=0.05$ level, i.e., the interaction term in the model is statistically significant, separate regression models will be refitted for each level of the factor. A forest plot will be used to display the results.

For secondary objective#3, the null hypothesis is that total event rates do not differ by treatment assignment, and the alternative hypothesis is that there is a difference in total event rates across treatment groups. We will use Generalize Linear Models (glm), namely Poisson regression, to model cumulative total of endpoint events with an offset for follow up time.

For secondary objective#4, the null hypothesis is that change in symptoms and suicidal ideation in the lithium group is similar to that of the placebo group. The alternative hypothesis is that there is a difference in change across treatment groups over time. We will use Generalize Linear Models (glm), namely Logistic regression, to model presence or absence of symptoms and suicidal ideation at each follow up visit, while allowing for random effects of variation in symptoms of bipolar disorder and depression at baseline.

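### The yes/no suicidal ideation endpoint has a look-back that lengthens when titration ends, and the SAP model has no term for it

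*SAP*

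**What the plan says.** SAP 5.2 makes ideation a binary variable for Objective 4: "presence or absence of suicidal ideation will be derived from the Columbia Follow Up Questionnaire" (form B6). SAP 5.3 then uses logistic regression "to model presence or absence of symptoms and suicidal ideation at each follow up visit", with random effects for baseline variation in symptoms. The alternative hypothesis is a between-group difference in change over time. No offset, interval covariate or fixed look-back is named. For the event counts of Objective 3, the same section does include an offset for follow-up time.

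Protocol Table 1 lists the monitoring instrument as "Columbia Scale -since last visit version, supplemented", and the Table 6 flowchart ties form B06 to that version at every follow-up visit. Protocol XIV (Titration Visits) sets assessments "every 10-14 days during the titration phase (in general, for up to six visits), and monthly until the end of study". Under Steady State Visits, "study visits will occur every month, with a window from one week before the target date to one week afterwards"; the completion visit may be up to one month late. Protocol XIII expects 4-6 titration visits for most participants, possibly fewer and up to 8. SAP 3.2 gives a different titration interval: "Titration visits will occur at intervals of 5-7 days over 3 months".

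**The concern.** A since-last-visit question asks about a longer period when visits are further apart, and a longer period gives more chance of a yes at the same underlying level of ideation. Reducing the answer to yes/no per visit, without recording how long it covers, mixes the visit calendar into the outcome.

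Two things are at stake. The described course of ideation over time would show a rise at the end of titration even if nothing changed. And because the length of titration, missed visits and early stopping all arise after randomisation, any difference between arms in these could appear as a treatment-by-time effect, which is what Objective 4 tests.

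**Working it through.** The documents give no ideation rate, power or expected effect for Objective 4, so there is no planned figure to reproduce. All ideation frequencies below are assumptions, shown as ranges.

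**Look-back lengths.** Titration: 10-14 days (12 used below). Steady state: about 30 days; with visits a week early or late, two successive visits can be 30 - 14 = 16 to 30 + 14 = 44 days apart. A completion visit one month late: about 30 + 30 = 60 days, at one visit only.

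**Step 1: short, independent episodes at a constant rate.** P(w) = 1 - exp(-λw), so P(30) = 1 - (1 - P(12))^(30/12).

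- P(12) = 10%: P(30) = 1 - 0.90^2.5 = 23.2%; odds ratio (0.232/0.768)/(0.10/0.90) = 2.7.
- P(12) = 20%: P(30) = 1 - 0.80^2.5 = 42.8%; odds ratio (0.428/0.572)/(0.20/0.80) = 3.0.
- Edges of the protocol interval, at a 30-day rate of 20%: 7.2% at 10 days and 9.9% at 14 days. At 7 days, the upper end of the SAP 3.2 interval, it is 5.1%, so that reading would enlarge the step.

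**Step 2: persistent ideation.** With point prevalence π and mean episode length m days, P(w) = π + (1 - π)(1 - exp(-aw)), where a = π/((1 - π)m).

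- π = 10%, m = 60: a = 0.10/(0.90 × 60) = 0.00185; P(12) = 12.0%, P(30) = 14.9%; odds ratio 1.3.
- π = 20%, m = 7: a = 0.20/(0.80 × 7) = 0.0357; P(12) = 47.9%, P(30) = 72.6%; odds ratio 2.9.
- π = 10%, m = 90: 11.1% at 10 days, 11.5% at 14 days and 13.3% at 30 days, so very long episodes nearly remove the step.

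Across steps 1 and 2 (12-day prevalence 10-20%, or π 5-20% with m 7-60 days) the odds ratio is about 1.3 to 3.

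**Step 3: effect on the between-arm test.** Simulated trials had 1,490 participants, 12-day titration gaps then monthly visits, gamma frailty (variance 1), no treatment effect and no time trend. There were 300 trials per setting. The model was a cluster-robust logistic regression on treatment, month and treatment × month, standing in for the SAP model.

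| Titration visits by arm | Spurious time slope (log-odds per month) | Time trend declared | False treatment × time |
|---|---|---|---|
| 5 v 5 | +0.077 to +0.081 | 100% | 2-7% |
| 4 v 6 | +0.077 to +0.081 | 100% | 29% (30-day rate 20%) to 42% (30-day rate 40%) |

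Adding log interval length as an estimated covariate took the slope to about 0.00 and the 4 v 6 rejection to 4-5%. Fixed 30-day windows also removed the slope, with treatment-by-time rejection no higher than about 8-9%, provided that window boundaries do not fall on the target visit dates.

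**Step 4: why not a fixed offset.** A complementary log-log model with log(days) as offset assumes independent episodes. Under the step 2 process with nothing changing, it reports a rate ratio of [-ln(1 - P(30))/30] / [-ln(1 - P(12))/12].

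- π = 10%, m = 60: (0.161/30)/(0.128/12) = 0.50.
- π = 20%, m = 7: (1.295/30)/(0.652/12) = 0.80.

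So it turns a spurious rise into a spurious fall.

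**The case against.** The strongest reply is that Objective 4 compares change between arms, and a step common to both arms is not a treatment difference. That stands: with equal schedules the simulated error rate was near nominal. The SAP also does not say how time enters the model, and a visit factor would absorb much of a common step. The 29-42% needs an assumed difference of 4 versus 6 titration visits, which the documents do not predict. Protocol XIII works against such a difference: placebo levels are simulated from dose, side effects and adherence, and the biostatistician periodically compares real and simulated distributions and revises the parameters. The objective is also declared exploratory and unpowered.

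A reader might infer that the bias runs against lithium, because Protocol Table 2 shows treatment-related attrition of 21% on lithium and 6% on placebo in the earlier placebo-controlled trial. The documents do not support this. The same table gives overall attrition of 58% and 59%. Protocol VII reports more discontinuation on placebo early on: 9.5% lithium against 16.7% placebo at 1 month, and 27.3% against 32.5% at 3 months. The direction is open.

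A reader might also infer that recorded ideation climbs throughout the year. It does not: the look-back is roughly constant once monthly visits begin.

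What remains is that the time course is distorted in any case, and the between-arm test has no protection if schedules differ.

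**Conclusion.** The concern holds in a limited form. The endpoint has a built-in upward step at the end of titration, with an odds ratio of about 1.3 to 3 for a 30-day against a 12-day look-back. The direction is certain for any stable ideation process; the size rests on assumed frequency and persistence. A real fall in ideation could mask it: with independent episodes, the rate would have to drop to between 10/30 = 0.33 and 14/30 = 0.47 of its titration value to cancel it.

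The treatment comparison is at risk only if titration length, missed visits or early stopping differ by arm, and then in either direction. The figure of about 29% assumes short episodes, a linear month term and 4 versus 6 titration visits; it shrinks if ideation persists.

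The point is confined to ideation, since the documents give no recall period for the Internal State Scale. The primary analysis is not affected.

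**What to change.** In SAP 5.3, Objective 4 (ideation), pre-specify one of the following.

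- **Fixed windows.** Collapse Columbia records into fixed 30-day windows counted from randomisation, scored as any ideation in the window, with each record assigned by its assessment date, before the logistic model. Place the boundaries midway between target visit dates (days 45, 75, 105 and so on, the first window running from randomisation to day 45). Otherwise a visit a few days early or late moves into the neighbouring window and part of the step returns. State that a window without a record is missing.
- **Interval covariate.** Keep the per-visit model and add log(days since the previous completed Columbia assessment) as a covariate with an estimated coefficient. Do not use an offset with its coefficient fixed at 1.

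State in either case how time enters the model. Reconcile the titration visit interval in SAP 3.2 with Protocol XIV.

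The cost is SAP wording and a few lines of code; the assessment dates are already collected. Collapsing into windows loses some titration-phase detail.

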Secondary objective (d) will be evaluated using mixed effect models allowing for random variation in symptoms of bipolar disorder and depression at baseline. The null hypothesis for this objective will be that change in symptoms and suicidal ideation in the lithium group is similar to that of the placebo group. The alternative hypothesis is that there is a difference in change across treatment groups over time.

Secondary objective (e) will be evaluated by regression analysis method comparing regression coefficients for treatment effect in the models with and without the mediator (Sobel, 1982), as well as by bootstrapping methods, (MacKinnon et al., 2002; Preacher & Hayes, 2008; Tein & MacKinnon, 2003).

Tertiary Data Analysis Plan

These exploratory objectives (explained further in Section XIV) are to analyze electronically available data over the extended follow up period to:

- (a) describe pattern of Lithium use following active participation in the study participants,
- (b) evaluate suicide reattempt and all cause mortality over a longer follow up period, both for the study population and patients who were evaluated for enrollment under HIPAA waiver (“pre-screen” population), and
- (c) evaluate all cause mortality over a longer follow up period.

Tertiary objective (a) will be evaluated by descriptive analysis on duration of lithium use, and by regression modeling to determine factors associated with any lithium use within one month following active study participation.

Tertiary objectives (b) and (c) will be evaluated using time to event survival analysis and Cox regression modeling to determine correlates of suicide reattempts and all cause mortality in the study population.

Data Repository

The Boston CSP Coordinating Center will create a data repository under the Boston IRB oversight for research purposes. Data will be housed at the Boston Cooperative Studies Program Coordinating Center and will be made available to appropriately credentialed researchers conducting studies related to suicide, lithium, or other health questions, in accordance with the Repository Protocol and relevant SOPs.

VIII. POTENTIAL PITFALLS OF THE PROPOSED DESIGN AND ALTERNATIVE DESIGN CONSIDERATIONS

Potential pitfalls of the trial include the threats to internal and external validity inherent in any clinical trial and those of particular concern to this study question.

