1. Minimizing dropouts: Several methods will be used to minimize dropouts. The study will maintain contact with study participants and reach out to those who do not follow-up. Contacts with treating physicians will be maintained and clinic appointment logs will be scanned to identify when participants will be visiting a VA facility for any reason. In addition, written permission to contact family members, friends, or others who would be likely to know the whereabouts of study participants will be obtained at enrollment. Study staff may arrange home visits to conduct interviews, when necessary, or offer assistance with transportation arrangements, and meal tickets.
 2. Participants who cannot tolerate study medication, even at reduced doses, will be encouraged to continue study assessments to allow their inclusion in the intention to treat (ITT) analyses and to allow our continued access to their electronic VA records.
 3. Analytic considerations: Estimates for dropout, and the probability of differential dropout are discussed in Section VII. For each secondary outcome, all data collected will be used in the repeated measures analyses. If missing data are determined to be informative, sensitivity analyses will be conducted to examine their influence on the treatment comparisons.

F. Safety concerns: Safety, obviously, is a primary concern. Our Safety Program has X essential elements

1. Lithium level monitoring that meets and/or exceeds what is done in usual care practice and VA practice. Labs are done centrally and reported as soon as they are done to the Safety Officer and *pari passu* to sites.
2. 24/7 availability of a Safety Officer, a senior psychiatrist, backed by a team with internal medicine, nephrology, cardiology experts – all blinded, are available for consultations on a case by case basis.
3. Safety first is the study's priority. This operationalizes a risk-adverse, conservative approach to study drug dosing. Summarized, when there is any doubt, we assume the subject is on active agent (lithium), treat reported or observed symptoms as potential lithium excess, and lower, or hold, or stop study medication (lithium/placebo) when there is any uncertainty or lack of data (lack of contact with subject, lab results, etc.)

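### Secondary Objective 4 tests change over time with, in effect, only a participant random intercept; its treatment-by-time test can be anti-conservative if within-person correlation decays or slopes vary

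*SAP*

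**What the plan says.** SAP Section 5.2 makes the Objective 4 outcomes binary. Symptoms come from the Internal State Scale (ISS) and ideation from the Columbia follow-up form. SAP Section 5.3 will use a generalised linear model, "namely Logistic regression, to model presence or absence of symptoms and suicidal ideation at each follow up visit", and adds the only dependence term: "while allowing for random effects of variation in symptoms of bipolar disorder and depression at baseline". The hypothesis in the same paragraph is about trajectories: "The alternative hypothesis is that there is a difference in change across treatment groups over time".

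Protocol Section VII covers the same objective, lettered (d), with "mixed effect models allowing for random variation in symptoms of bipolar disorder and depression at baseline". Protocol Section VIII, item E, adds: "For each secondary outcome, all data collected will be used in the repeated measures analyses".

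Neither document names the participant as the random-effect subject, and neither gives a random slope, a serial covariance or a robust variance. The SAP prints SAS code for the primary model and the site frailty model but none for this objective, so code does not settle the point. SAP Section 5.1 calls all the secondary objectives exploratory and not powered.

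**The concern.** The participant is randomised, but the data for this objective are participant-visits. A completer contributes well over a dozen binary records per outcome. A random intercept makes every pair of a participant's visits equally correlated on the logit scale and gives everyone the same time course apart from a level shift. Mood symptoms and ideation may well depart from both: neighbouring visits tend to be more alike than distant ones, and people improve or worsen at different rates. Where that happens, part of the variation in individual time courses is missing from the model-based standard error of the treatment-by-time term.

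At stake is a reported effect of lithium on the course of symptoms or ideation with an interval that is too narrow. Protocol Section XX plans a paper on lithium's effect on mood symptoms in these patients, so the intervals are likely to be published.

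**Working it through.** **1. Is there a figure to reproduce?** No. The plan gives no alpha, power, variance or correlation for Objective 4. A two-sided 0.05 is assumed below.

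**2. Records per completer (protocol Table 6; titration and Month 2 rules in Section XIII).**
- ISS: T1 and T4 (2) + Months 2 to 11 (10) + End of Study (1) = 13 post-baseline, or 14 with the 30-day visit.
- Columbia: with six titration visits, 6 + 10 + 1 = 17, or 18 with the 30-day visit. With four titration visits, 4 + 10 + 1 + 1 = 16. With eight, and Month 2 omitted after a long titration, 8 + 9 + 1 + 1 = 19. So about 16 to 19.

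**3. What the model assumes.** For participant i at time t:

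logit P(Y = 1) = b0 + b1·t + b2·trt + b3·trt·t + u_i, with u_i ~ N(0, s²).

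The tested contrast is b3. Between visits j and k, the latent covariance is:
- random intercept only: s², whatever the gap;
- with an independent random slope (SD s1): s² + t_j·t_k·s1²;
- with an added AR(1) process (SD a, monthly correlation r): s² + a²·r^|t_j − t_k|, with t in months.

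A random-intercept fit has no place for the extra term in the second and third cases.

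**4. Size, by simulation with no treatment effect.** Assumed inputs: 300 participants, 14 post-baseline visits on the ISS schedule, random-intercept SD 1.5 (latent intraclass correlation 2.25/(2.25 + 3.29) = 0.41), 4,000 replicates, Wald test of b3 at 0.05. The Monte Carlo SE at 5% is √(0.05 × 0.95/4000) = 0.003.

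| True within-person structure | Random-intercept logistic | Plain logistic, no participant term | Logistic, participant-clustered sandwich SE |
|---|---|---|---|
| Constant correlation | 0.046 | 0.019 | 0.046 |
| AR(1) SD 1.0, r = 0.5 | 0.073 | 0.037 | 0.049 |
| AR(1) SD 1.0, r = 0.8 | 0.096 | 0.046 | 0.047 |
| AR(1) SD 1.5, r = 0.8 | 0.140 | 0.080 | 0.055 |
| Slope SD 1.0 logit/year | 0.076 | 0.036 | 0.050 |
| Slope SD 2.0 logits/year | 0.128 | 0.067 | 0.050 |

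**5. Second simulation, different settings.** Here there were 13 monthly records, intercept SD 1.8 (3.24/(3.24 + 3.29) = 0.50), a shared decline of 0.5 logit per year, 500 replicates (Monte Carlo SE about 1 point) and a likelihood-ratio test. The random-intercept model rejected in 5.0% with no slope variation, and in 6.6%, 10.4% and 16.4% with slope SD 1, 2 and 3. It rejected in 11% to 12% with AR(1) correlation 0.80 to 0.95. Participant-clustered errors gave 3.2% to 5.2% for the same contrast.

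**6. Does the simulated sample size matter?** Little. The model-based variance and the omitted component both shrink in proportion to 1/n, so their ratio does not improve as the trial grows.

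**Limit of the check.** The clustered-variance results are for a marginal logistic model. A mixed model with a random slope and an empirical variance, as proposed below, was not itself simulated.

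**The case against.** **The plan does model within-person dependence.** A reader might infer from the SAP's generalised-linear-model wording that repeated records are treated as independent. The documents do not support that. The SAP sentence itself says random effects, and the protocol specifies mixed-effects models and repeated-measures analyses. For ideation, the SAP ties the random effect to mood symptoms, but the Covariates paragraph in protocol Section VI counts suicidal ideation among affective symptoms. The sentence is loose, and a participant intercept for both outcomes is the natural reading. Nor would the independence reading show an inflated treatment-by-time test. The plain model fell below 5% in four of the six scenarios; what it inflates is the treatment main-effect term (14% to 19%). This objection stands.

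**Inflation is not certain.** Under constant correlation the planned test is valid (4.6% and 5.0%). The larger figures need substantial heterogeneity: a slope SD of 2 or 3 logits per year means a one-SD change in odds of e² ≈ 7-fold or e³ ≈ 20-fold over the year. At slope SD 1, the rates are only 6.6% and 7.6%. This also stands, and it limits the point to a conditional one.

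**The objective is exploratory.** No alpha is stated for it and no trial decision depends on it. That lowers the weight, but formal hypotheses are written for it and a paper is planned, so interval width still matters.

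**Mediation.** A reader might also infer that the error carries into Objective 5. It does not: SAP Section 5.3 compares Cox treatment coefficients with and without the mediator and does not use the Objective 4 test.

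**Conclusion.** The concern holds as a conditional one. Read as a whole, the plan is a random-intercept logistic model applied to a treatment-by-time question. Its test is sound if within-person correlation is constant and participants share a time course, and can be anti-conservative otherwise: about 7% to 14% false positives at nominal 5% under AR(1) monthly correlation of 0.5 to 0.8 (SD 1.0 to 1.5) or slope SD 1 to 2 logits per year. Those inputs are assumptions. The direction is well supported, but the size in this trial is unknown. The documents do not support saying outright that serial dependence is ignored or that the test is anti-conservative. The effect is confined to an exploratory objective; the primary log-rank test uses one first-event time per randomised participant and is untouched.

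**What to change.** In SAP Section 5.3, keep the mixed logistic model for Objective 4 and specify, for each outcome:
- the participant as the random-effect subject, for symptoms and for ideation alike;
- a participant random slope for time, or a serial covariance, in addition to the intercept;
- an empirical (sandwich) variance estimator clustered on participant;
- adjustment for the baseline value of that same outcome;
- treatment-by-time as the tested contrast.

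Bring protocol objective (d) into line.

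A GEE with sandwich errors is suitable as a sensitivity analysis rather than as the main model. It estimates a marginal instead of a participant-specific effect. The plan also allows for up to 40% dropout, and unweighted GEE generally needs a stronger missing-data assumption than the mixed model does. It should therefore be paired with weighting or with the multiple imputation that protocol Section VII already foresees for longitudinal outcomes.

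The cost is a paragraph of SAP text, a few lines of SAS and slightly more analysis work, with somewhat wider intervals. No new data are needed.
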